Calculations of sample size were based on the primary endpoint of WOMAC-PF at 3 months. We propose to recruit a total of 240 subjects (96 in each exercise arm and 48 in the usual care group) to allow approximately 86 subjects in each exercise arm and 43 in the usual care group available for a complete case analysis at 3 months (assuming 10% attrition at 3 months). We propose a larger number of subjects in both exercises groups (outpatient rehabilitative exercise and community-based group exercise) because we expect a moderate effect size between these two interventions; whereas we propose a smaller number of subjects in the usual care group because we expect a large effect size between the usual medical care group and either of the exercise groups. Thus, with an alpha level of 0.05, 2 tails test, a sample size of 172 (n=86 in each exercise group) will provide 81% power to detect a difference as small as 3.3-point difference between the two exercise groups in WOMAC-PF (SD of 7.7 from our pilot work).¹¹ This would correspond to a difference in less than 2 activities (out of the 17 queried in the WOMAC-PF) having improved from “about moderate difficulty” to “no difficulty”. The sample size of 43 in the usual medical care group will provide 80% power to detect a difference of 5.2-point difference in WOMAC-PF between the usual medical care group and any exercise group. Power analysis was conducted in NCSS/PASS. Moreover, this sample size will provide adequate power (above 80%) to test the hypothesis related to the secondary outcomes (performance-based physical function and physical activity). For example, we will be able to detect differences between the two exercise groups as small as 0.7 sec in the stair climbing test, 0.4 in the chair-rise test, 0.02 m/sec in walking speed, 1.4 sec in the single leg stance, and 35 min/day in light intensity physical activity (based on SD of our own preliminary data). The differences we will be able to detect between the usual care and any intervention groups are as small as 1.01 sec in the stair climbing test, 0.54 in the chair-rise test, 0.03 m/sec in walking speed, 1.6 sec in the

PRINCIPAL INVESTIGATOR (LAST, FIRST, MIDDLE): [name]

single leg stance, and 49 min/day in light intensity physical activity. These differences are smaller than the known minimal detectable changes for these outcomes.⁸⁸⁻⁹⁰

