During our pilot study 100% of the patients completed the 2 month follow-up assessment;¹¹ however we are realistic and recognize that such retention rate is very optimistic for this study. Thus, in this study we estimate the attrition to be 10% at the 3 months follow-up. We also estimate the attrition to be 15% at 6 months, based on our pilot work and other studies with similar populations and timeframes. We will compare baseline characteristics between patients with and without the assessment at 3 and 6 months to assess potential biases in the complete case analysis. We will also try to obtain reasons for study drop out to assess the missing data mechanism (missing completely at random, missing at random, non-ignorable missingness). We will use several missing data methods for imputing data and re-analyze using intention to treat (as randomized) to assess the impact of missing data on our conclusions as recommended.⁹⁷ We

PRINCIPAL INVESTIGATOR (LAST, FIRST, MIDDLE): [name]

will first use multiple imputation (with M=10 imputations) which assumes the data are missing at random. Since the data could be missing not at random, we will use another approach of assigning the lowest observed scores for missing values differentially by treatment group (non-ignorable missingness). The approach assumes the missingness is directly related to the value of the missing data, i.e., the people who are missing data on function have worse function scores (did not come in for assessment because function was worse). Results of all approaches to missing data will be presented in the primary paper for our study. If our significance and interpretation of our treatment effect vary depending on the method of imputation, we will view any conclusions cautiously.

PATIENT POPULATION

Detailed reasoning of inclusion criteria is provided in Human Subjects.

Subjects will be included in the study if they underwent a unilateral TKR 2 to 4 months prior to study, are older than 60 years of age, experience functional limitation in daily activities (score in the WOMAC-PF of at least 9 points), *speak English sufficient to understand study instructions*, are willing to be randomized to one of the 3 treatment groups, and have medical clearance to participate in the study.

Subjects will be excluded if they:

- Have absolute or relative contraindications to exercise testing as established by the American College of Cardiology/American Heart Association;^{99,100}

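### The only missing-not-at-random analysis fills each arm's dropouts with that arm's extreme observed score; even with its direction corrected, it can remove significance when dropout is harmless

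*Combined protocol and SAP*

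**What the plan says.** The section on dropout and missing data analyses sets two imputation analyses beside the primary mixed model.

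- The first is "multiple imputation (with M=10 imputations) which assumes the data are missing at random".
- The second is "assigning the lowest observed scores for missing values differentially by treatment group (non-ignorable missingness". Its stated reasoning is that people with missing function data have worse function.

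No size of departure from missing at random, range of departures or tipping point is given. All approaches are to be reported in the primary paper, with this consequence: "If our significance and interpretation of our treatment effect vary depending on the method of imputation, we will view any conclusions cautiously".

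Under Hypothesis 1.1, the primary analysis is an intention-to-treat linear mixed model of 3- and 6-month scores. The main interest is the 3-month comparison of the two exercise arms. The Physical Function section says that WOMAC-PF runs from 0 to 68 and that higher is worse.

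**The concern.** The direction of the rule is one problem: on WOMAC-PF the lowest score is the best function. This point is about what remains once that is put right.

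On its natural reading, every dropout in an arm then receives the worst score observed in that arm. Three things follow.

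- About a tenth of each arm sits at one far value, which widens the spread.
- That value comes from a single patient, so it differs between arms by chance.
- An arm with more dropouts is pushed further, whatever the reason for dropout.

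Multiple imputation under missing at random makes the same broad assumption as the mixed model. The planned imputations therefore examine either no departure from that assumption or an extreme one. Because a change in significance calls for caution, a check that often changes significance under harmless dropout cannot separate a fragile result from a robust one.

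**Working it through.** **Inputs (Sample Size section).** "with an alpha level of 0.05, 2 tails test"; "SD of 7.7 from our pilot work"; randomised "96 in each exercise arm and 48 in the usual care group"; analysed "approximately 86 subjects in each exercise arm and 43 in the usual care group", from 10% attrition. The plan states that this "will provide 81% power to detect a difference as small as 3.3-point difference between the two exercise groups in WOMAC-PF".

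**The plan's own figure.** SE = 7.7 × √(2/86) = 1.174. Then 3.3/1.174 = 2.81, and power = Φ(2.81 − 1.96) = 80.2% (noncentral t: 79.8%). This agrees with the stated 81% to within about a point.

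**Assumptions not in the documents.** The documents give neither the mean nor the shape of the 3-month scores. Both normal and right-skewed (gamma) scores were tried. Dropout was completely at random, so the observed-data result is sound. Each missing score was set to the highest observed score in its own arm, and a two-sample t-test was run on 8,000 to 10,000 simulated trials per setting.

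**1. Variance.** With 10 of 96 imputed, f = 10/96 = 0.104. If the worst score lies D points above the observed mean, the arm variance becomes about (1−f) × 7.7² + f(1−f) × D² = 53.1 + 0.0933 × D².

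- Normal scores: the simulated pooled SD is 9.3, which implies D = √[(86.5 − 53.1)/0.0933] ≈ 18.9. The SE becomes 9.3 × √(2/96) = 1.34, and power is about Φ(3.3/1.34 − 1.96) = 69%. The simulations gave 67-70%.
- Skewed scores: the pooled SD is 10.5-11.5 and the simulated power 47-57%.

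**2. Significant results that lose significance (10% dropout, true difference 3.3).**

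| Setting | Normal | Skewed |
|---|---|---|
| Exactly 10 dropouts per arm | about 15% | 30-41%, by degree of skew |
| Dropout counts varying by chance | about 20% | about 33% |
| Baseline-adjusted ANCOVA, 10 per arm | 14-16% | 35-37% |

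At a true difference of 5, the loss is about 3-6% (normal) and 13-16% (skewed).

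**3. Dependence on one patient.** Each point on an arm's worst score moves that arm's mean by 10/96 = 0.10 through the imputed values. With counts fixed, the estimate moves by a random amount with SD about 0.49 (normal) to 1.00 (skewed). If the second-worst patient supplies the value in one arm or the other, the significance verdict changes in 16% (normal) or 25-29% (skewed) of trials.

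**4. Dependence on dropout counts.** When counts vary by chance, the SD of the shift rises to 0.95 (normal) or 1.47 (skewed), against the primary SE of 1.17. With harmless dropout of 7.5% v 12.5%, the mean shift is about (0.125 − 0.075) × D. For normal scores that is 0.05 × 18.9 = 0.94; the simulations gave 0.92 (normal) and 1.26 (skewed), which is 28-38% of 3.3. If the better arm loses more patients, 47-60% of significant findings are lost.

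**5. No true difference.** With counts varying, the rule gives false positives in about 8-12% of trials instead of 5%. A rerun with exactly 10 dropouts in each arm stayed close to 5%, so the excess comes from unequal counts.

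**6. Comparison method.** Delta-adjusted multiple imputation (M=10, Rubin's rules), with dropouts in both arms made worse by 0, 3.3 or 7.7 points, lost only about 2-4.5% of significant results. Unequal shifts would move the result further, by design and by a stated amount.

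**The case against.** **It is only a stress test.** A pessimistic analysis is meant to be conservative, and the mixed model stays primary with every version reported. This stands. A reader might infer that the analysis decides the trial's conclusion, or that the result hangs on one patient per arm. The documents support neither: the consequence is caution, and about 90% of the scores are observed. Only the imputed value rests on one patient.

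**Much of the instability comes from dropout counts.** This also stands. For normal scores, fixing the counts cuts the SD of the shift from 0.95 to 0.49, so about three quarters of the variance is due to counts (1 − 0.49²/0.95² = 0.73). That is still a fault of the rule, because the counts here carry no information about treatment.

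**The loss rates depend on chosen settings.** A difference of 3.3 with 80% power leaves many p-values near 0.05, and the skew is assumed. Both are correct, hence the ranges.

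**The figures describe a corrected rule.** True. Taken literally, with the lowest score assigned, skewed scores floored at 0 give only 0.4-6% losses and normal scores 14-18%. But the literal rule contradicts its own stated reasoning and has to be rewritten in any case.

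**Larger arms have a more extreme worst score.** A reader might apply this to the main comparison. It does not apply there, because both exercise arms have 96; it bears only on comparisons with usual care.

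**Other steps are planned.** The plan compares baseline characteristics by missingness and collects reasons for dropout. These help to interpret an extreme result, but they do not supply a graded analysis.

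**Conclusion.** The concern holds as a worthwhile improvement to a sensitivity analysis; it is not a flaw in the primary analysis. With its direction corrected, the rule removes significance from about 15-20% (normal) to about one third (assumed skew) of significant results at a true difference of 3.3, and from about 5-15% at a difference of 5, when dropout is 10% and harmless. Harmless dropout of 7.5% v 12.5% shifts the estimate by 0.9-1.3 points.

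These figures rest on 96 v 96, SD 7.7, dropout completely at random, an assumed score shape, and a t-test or ANCOVA standing in for the mixed model, without 6-month data. The practical effect is that the clause on cautious conclusions can be triggered without cause, while multiple imputation under missing at random tests no departure from the primary model's assumption.

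**What to change.** Make one edit to the section on dropout and missing data analyses, together with the correction of direction.

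1. Replace the extreme-value rule with delta-adjusted multiple imputation by arm. Impute WOMAC-PF under missing at random from baseline and attendance data. Use the 1.5- and 4.5-month calls only where available: Table 1 schedules them for adverse events and co-interventions, and people who have dropped out may have no call data.
2. Make the imputed values worse (higher) by a pre-specified range of shifts, for example from 0 to about one SD (7.7 points), varied separately by arm. The documents do not fix this range, so the team must choose and justify it.
3. Report the tipping point at which the 3-month clinic v community conclusion changes.
4. Apply the clause on cautious conclusions according to whether that tipping point is clinically plausible.

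Using one pooled worst score for all arms would not help: about 30% (normal) to 47-59% (skewed) of significant findings would be lost.

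The cost is revised wording, a little more programming and a judgement on the shift range. No new data are needed.
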